### **b. Specific**

1. To compare the concentrations of appetite hormones when consuming a coffee and agave inulin-based beverage vs a control beverage.
2. To compare the subjective sensations of appetite when consuming a coffee and agave inulin-based beverage vs a control beverage.
3. To compare the dietary intake when consuming a coffee and agave inulin-based beverage vs a control beverage.
4. To compare the biochemical profile when consuming a coffee and agave inulin-based beverage vs a control beverage.

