## **HYPOTHESIS**

A beverage based on coffee and agave inulin modifies appetite, dietary intake, and biochemical profile in subjects with obesity.

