**f. Sample size calculation**

The information reported in the article by Rahat et al., which had a double-blind randomized crossover design, was used to calculate the sample size (13). In this study, a significant

increase in the active PYY response was found when consuming 24 g of inulin mixed with 75 g of glucose dissolved in water (increase in the area under the curve from 0 to 4 h (iAUC04) = 5.69 pmol×h/L ± 9.8 pmol×h/L), compared with consumption of only 75 g of glucose dissolved in water ((iAUC04) = 1.06 pmol×h/L ± 10 pmol×h/L) with a p=0.003.

The program G\*Power v.3.1.9.7 (36) was used for the sample size calculation, and an n=24 was obtained using the formula for dependent mean difference and considering a loss of 25% (which is common in this type of study); 30 subjects would be required for this project.

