##### *Dependent variables*

Appetite hormones

Subjective appetite sensations

Dietary intake

Biochemical profile

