## Appetite assessment

### Appetite hormones

The hormones and peptides ghrelin are measured in their acetylated form (Biovendor brand kit, catalog #: RA194062400R), GLP-1 (Biovendor brand kit, catalog #: YK160), and PYY (Biovendor brand kit, catalog #: YK080 ), by an ELISA assay and using a Thermo Scientific brand Multiskan Sky spectrophotometer.

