### Subjective sensations of appetite

The subjective sensations of appetite consist of 9 questions that are asked in the fasting state and after drinking the beverage. Specifically, 30 minutes before drinking the beverage, immediately after consuming it, 30 and 60 minutes after consumption. These scales assess hunger, fullness, satiety, desire to eat, prospective consumption, and the desire for sweet, salty, fatty, and savory foods. Visual analogue scales are made up of lines, usually 100 mm long, with the term “None” or “Not at all” at one end and “Yes, very much” at the other end. or "As much as I have never felt." The subject marks a point between these two extremes, and the quantification is done by measuring the distance from the left end of the line to the mark to which a score is given (49).

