## **Biochemical profile**

### Blood sample collection

Of the 6 sessions that the participants attend, two blood samples will be taken at the beginning and end of each phase, that is, in 4 sessions.

The first is in the morning, after 8 to 12 hours of fasting by venipuncture, and later 30 minutes after ingestion of the beverage. Two red and one purple vacutainer tubes are obtained, each with 5 ml of blood, centrifuged at 3500 rpm for 15 minutes at 4°C to separate the serum and plasma.

The serum will be used for glucose and lipid profile determinations, the plasma will be used for determining appetite hormones,

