#### Statistical analysis

Quantitative variables will be expressed as mean  $\pm$  standard deviation or median and interquartile range for descriptive statistics, and qualitative variables as frequency or percentage. The normality of the variables is evaluated with the Shapiro-Wilk test. The general linear mixed model will be used to compare the two treatments. The data will be emptied into an Excel spreadsheet to be later imported into the SPSS v.21 program for analysis, considering a value of  $p < 0.05$  as statistically significant. The graphs will be made with Graphpad software version 9.3.1.

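### The protocol names no primary outcome, and the only sized quantity, the 0–4 h PYY area, cannot be formed from its blood draws and so cannot stand in for one

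*Protocol*

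**What the plan says.** The general objective covers beverage characteristics, appetite, dietary intake and biochemical profile together. Under it, the Specific objectives are four separate comparisons with the control beverage. The first is "To compare the concentrations of appetite hormones when consuming a coffee and agave inulin-based beverage vs a control beverage"; the others concern subjective appetite, dietary intake and biochemical profile. They are numbered, but nothing says that the numbers are a ranking. The Hypothesis joins three domains in one sentence: "A beverage based on coffee and agave inulin modifies appetite, dietary intake, and biochemical profile in subjects with obesity". The Dependent variables section lists four families side by side, one of them "Subjective appetite sensations". The word primary is not attached to any of them.

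The Statistical analysis section names one general linear mixed model for comparing the two treatments and one criterion, "considering a value of $p < 0.05$ as statistically significant". Neither is tied to a particular outcome.

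One outcome has a special place. The Sample size calculation rests on active PYY from a cited crossover study, summarised as the incremental area under the curve over 0 to 4 hours. Under Blood sample collection, the trial's own samples are taken "after 8 to 12 hours of fasting by venipuncture, and later 30 minutes after ingestion of the beverage", in four of the six sessions, and the plasma goes to the hormone assays.

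**The concern.** A protocol should let a reader say in advance which single result decides the main question. Here four families of outcomes stand level and share one threshold. The usual fallback is to take the sized outcome as the implied primary, and that fails because the sized quantity is not one the trial will have.

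Two things are at stake. First, any hormone, appetite, intake or biochemical result below 0.05 could later be put forward as the main finding for its domain, and nothing in the protocol would show otherwise. Second, the planned number of participants is justified for a quantity that the trial does not produce. The power for whatever is eventually treated as the main comparison is therefore unknown.

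**Working it through.** **1. Is any outcome singled out?**

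| Section | Content | Ranking |
|---|---|---|
| Objective | Beverage characteristics, appetite, dietary intake, biochemical profile | None |
| Specific objectives | Four comparisons with control | Numbered only |
| Hypothesis | Three domains in one sentence | None |
| Dependent variables | Four families | None |
| Statistical analysis | One model, one threshold | Not tied to an outcome |

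**2. The plan's own sample size.** The inputs, all from the Sample size calculation, are means of 5.69 and 1.06 pmol×h/L, SDs of 9.8 and 10, the formula for dependent means, n = 24, a 25% loss and 30 to be recruited.

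- Difference: 5.69 − 1.06 = 4.63.
- SD of the paired difference: √(9.8² + 10² − 2·ρ·9.8·10), where ρ is the within-person correlation.

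Neither ρ nor the power is stated, so n = 24 can be matched only by assuming both. At ρ = 0.70 the SD is 7.67 and the standardised difference is 4.63 / 7.67 = 0.604. A two-sided 0.05 paired t-test then needs n = 24 for 80% power (power 0.808 at 24). At ρ = 0.5 the same test has 59% power with 24 and needs 38. The step to 30 equals 24 × 1.25. So the figure of 24 is attainable, but every input to it refers to the 0–4 h PYY area.

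**3. Can the trial form that quantity?**

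| | Sample size calculation | Blood sample collection |
|---|---|---|
| Measure | Incremental area under the curve | Concentrations at two draws |
| Time span | 0 to 4 h | Fasting and 30 min after the beverage |

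Two draws, the later one 30 minutes after the beverage, cannot give an area to 4 hours.

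**4. Could PYY still be primary in some other form?** The objective speaks only of hormone concentrations. The Appetite hormones section lists three: acetylated ghrelin, GLP-1 and PYY. Each is sampled twice per session in four sessions. For PYY alone the treatment contrast could be the fasting level at the end of a phase, the 30-minute level, or the rise from fasting to 30 minutes on the first or the last day. None is chosen. Even a reader who accepts PYY cannot write down the one comparison to be tested.

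**5. Illustrative size.** Assume one test per objective, four in all, each two-sided at 0.05, with no true effect and no adjustment.

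- Independent tests: 1 − 0.95⁴ = 1 − 0.8145 = 0.185.
- Common correlation r: 1 − ∫ φ(u)·[Φ((1.96 − √r·u)/√(1−r)) − Φ((−1.96 − √r·u)/√(1−r))]⁴ du, evaluated numerically.

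| Assumed r | Chance of at least one p < 0.05 |
|---|---|
| 0 | 18.5% |
| 0.5 | 15.6% |
| 0.7 | 13.0% |
| 0.8 | 11.4% |

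The protocol gives no correlations, so every value of r is an assumption.

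**The case against.** The strongest reply is that the protocol commits no error of statement. A 0.05 threshold is conventional. The hypothesis reads as one joint claim, and if all three domains had to succeed, error would not be inflated in this way. A trial of a little-studied combination may have several objectives of equal standing. A multiplicity procedure may sit in an analysis plan that is not shown.

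Much of this stands. The Statistical analysis section does not say that p-values will go unadjusted, and a reader who infers that goes beyond the text. The percentages above are therefore conditional and do not describe what the trial will do. The joint reading is possible, but the Hypothesis does not require every domain to succeed, and the Specific objectives set separate comparisons that can each be reported alone. If the trial is meant to be exploratory, it does not say so.

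A reader might also count each of the three hormones and nine appetite scales as its own test. That gives 1 − 0.95¹² = 46.0% under independence. The documents do not support this as the size of the problem: no section makes each scale a separate claim of success, and ratings from the same person are unlikely to be independent.

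Finally, it may be said that PYY is measured, so the sizing still points to it. PYY concentration is indeed measured. What is missing is the sized summary of it and any choice of contrast to replace that summary. The figure showing session procedures is not available, but the text on blood sampling is explicit about the two draws.

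**Conclusion.** The point holds in a limited form. The protocol designates no primary outcome, and the only sized quantity cannot fill the gap because the sampling schedule cannot produce it. No analysis plan could repair the second part without a change to either the Sample size calculation or the Blood sample collection section.

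The illustrative size is 18.5% for one test per objective if independent, 13.0% at a correlation of 0.7 and 11.4% at 0.8, against a nominal 5%. These figures rest on an assumed count of four tests, assumed correlations and no adjustment. They show why a designation matters and are not a forecast of the trial's error rate.

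The documents do not show that results will be reported selectively, that no adjustment is planned, or that PYY is not assayed. The change should be made, but it need not hold up the conduct of the trial.

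**What to change.** Before unblinding, the investigators should:

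- Name, in the Specific objectives and in Statistical analysis, one primary outcome at one contrast that the trial measures: the variable, the session, the time point or change, and intervention versus control beverage. The choice is theirs.
- State that this contrast is tested at 0.05 and is the only confirmatory claim.
- Label all other outcomes secondary or exploratory. How multiplicity among them is handled can be left to the analysis plan.
- Restate the Sample size calculation for the chosen measure, giving the power or the detectable difference at the planned n, with the assumed SD and within-person correlation.

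The cost is a few lines of text and one recalculation. No further participants are required. The downsides are that secondary results can no longer be presented as confirmatory, and that the restated power may be less favourable than the present calculation suggests.

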### **VIABILITY**

#### **a. Financing**

This project is funded by “Fondo para Proyectos de Impulso a la Investigación, 2022 III”.

#### **b. Infrastructure**

There is access to the 2 study sedes and collaboration with the researchers responsible for the laboratories and hospital. These spaces already have the necessary equipment to carry out this project.

#### **c. Human resources training**

This research project will train two PhD students in Translational Nutrition Sciences and two undergraduate students. Furthermore, given its scope, it will allow the acceptance of professional internships and social service students.

